### Safety endpoints

Not applicable

### Stopping rules and discontinuation

Not applicable:

Page **11** of **29** Final version 8 –18 May 2015

This is an adaptive complex intervention and management of participants with gout will continue through the 24 month period unless any participant opts to leave the study. Patients who experience adverse events relating to drug therapy for their gout will have the responsible ULT stopped and an alternative ULT considered. Because of its adaptive nature (i.e. not monotherapy) there is no contingency for early withdrawal from the trial in terms of efficacy or futility of a specific individual treatment.

### **RANDOMIZATION**

At the initial visit the nurse will answer any further queries concerning the study and obtain written consent to participate. Random allocation will be undertaken using computer generated random numbers. Immediately following written consent, the nurse will phone into Academic Rheumatology, the administrative team will generate the group allocation via the website. Once allocated the patient will be informed of which group they are in. The study number will be used as the patient ID to de-identify the patient information throughout the study.

### Maintenance of randomisation codes and procedures for breaking code: Not applicable:

The study team will be made aware of whether the individual has been randomised into the nurse Intervention arm or the control arm of the RCT at the outset to enable the appropriate initial consultation and to arrange follow up of those in the nurse-led intervention group.

### TRIAL MANAGEMENT

The trial will be coordinated by the research team in Academic Rheumatology, led by [name], Chief Investigator. The Project Manager, will manage recruitment and the day to day running of the trial.

There will be a Trial Steering Committee. Membership of the Steering Committee is to be approved by the funders Arthritis Research UK and will include:

- an independent Chairperson (not involved directly with the study other than as a member of the Steering Committee)
- two or more other independent expert members (clinical and/or methodological)
- the Chief Investigator
- if possible a lay/consumer representative
- an observer from Arthritis Research UK

The Steering Committee will have an initial meeting to finalise the protocol then will meet again 3 months after the start of the study and then approximately every 6 months. The CI will keep the committee informed of recruitment progress at regular intervals (monthly) throughout the recruitment phase.

The Steering Committee will monitor and supervise the progress of the study and advise on recruitment rate and unforeseen logistical issues to ensure that its objectives are achieved.

Page **12** of **29** Final version 8 –18 May 2015

### **DURATION OF THE TRIAL / STUDY AND PARTICIPANT INVOLVEMENT**

The total study duration will be 3 years, 8 months recruitment, 2 years participation and 4 months analysis and writing up. Each participant will be in the study for 2 years from the point of entry.

### **End of the Trial**

The study will end following the last visit of the last participant.

# SELECTION AND WITHDRAWAL OF PARTICIPANTS Recruitment

Participants will be recruited from collaborating GP surgeries and via advertisements/promotion in the media (local newspapers, radio and TV and via the internet) and posters placed on noticeboards approved for this purpose in the local community (e.g. community centres and patient waiting areas in NHS facilities).

### Recruitment via collaborating GP surgeries

Staff at the GP's surgeries will be asked to identify patients with gout from their lists and send them a questionnaire together with covering letters from their GP practice and the CI. The questionnaire will enquire concerning their gout (including any acute attacks in the previous year), current drug treatments, comorbidities, QOL, and willingness to receive information on an additional study relating to management of gout. The questionnaire should take approximately 30 minutes to complete. Patients will be asked to return their questionnaires to Academic Rheumatology and the relevant data will be extracted to enable them to be identified as suitable for the trial. GP surgeries will be asked to send one reminder if a reply is not received within 3 weeks.

Suitable patients who indicated willingness to be informed of a management trial will be sent a letter and information sheet concerning this. Approximately 10 days after posting the information to the patient, the research team in Academic Rheumatology will telephone them to answer any questions they may have and, if they have decided they wish to participate, confirm their eligibility. If they respond positively a mutually convenient appointment will be arranged, at the patient's GP's surgery. The research nurse will inform the participant or their nominated representative (other individual or other body with appropriate jurisdiction), of all aspects pertaining to participation in the study.

### Recruitment via advertising campaign

Gout sufferers who contact the department in response to an advertisement will be asked a few questions to confirm the diagnosis of gout and that they have experienced an attack of gout in the previous 12 months. Patients who are eligible to participate will be sent an information sheet and again, the study team in Academic Rheumatology will contact them approximately 10 days later to ask if they have any further questions and if they wish to participate. If they respond positively a mutually convenient appointment will be organised to see the patient at home. If a patient specifically requests an appointment at an alternative location, attempts will be made to arrange to see the patient at their GP's surgery.

Page **13** of **29** Final version 8 –18 May 2015

As this study aims to determine, the effectiveness and cost effectiveness of a nurse-led complex intervention in community-based patients with gout, all participants will be seen, by research nurses, at their GP practice or in their own homes (i.e. not in a hospital setting).

If needed, the usual translator services will be available to assist with discussion of the trial, the participant information sheets, and consent forms, but the consent forms and information sheets will not be available printed in other languages. It will be explained to the potential participant that entry into the trial is entirely voluntary and that their treatment and care will not be affected by their decision. It will also be explained that they can withdraw at any time but attempts will be made to avoid this occurrence. In the event of their withdrawal it will be explained that their data collected so far cannot be erased and we will seek consent to use the data in the final analyses where appropriate.

### Inclusion criteria:

- All Adults aged 21 and over with a GP given diagnosis of gout, confirmed following telephone interview to ensure that participants fulfil ACR criteria for gout.
- Nurse intervention and standard care groups (RCT) at least one acute attack of gout in the previous year.

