### TRIAL / STUDY OBJECTIVES AND PURPOSE

### **PRIMARY OBJECTIVE:**

To determine in community-based patients with untreated or under treated gout the effectiveness and cost effectiveness of a nurse-led complex intervention compared to standard GP led care.

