### **Primary endpoint:**

Percentage of patients who hit the therapeutic target at end of year 2 (SUA <360 µmol/L)

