### **Exclusion criteria**

- Inability to give informed consent
- GPs will be asked not to contact people with terminal or mental illness

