### Power calculations:

Information that includes SUA on community-derived patients with gout is sparse. However, detailed information on frequency of attacks, treatment, SUA and quality of life is available for 250 gout patients from 17 practices in Nottingham (5, 11). In this survey: 30% of patients were on ULT; the rate for acute attacks in the previous year was 32% for patients on ULT and 57% for patients on no ULT; mean SUA was 318  $\mu$ mol/L in those taking ULT compared to 434  $\mu$ mol/L in those not taking ULT; and 23% of those taking ULT had a SUA >360  $\mu$ mol/L, compared to 75% of those not on ULT. For quality of life (SF36) overall mean and SD for those on ULT was 16.41 (2.81) compared to 15.67 (3.05) for those not on ULT, giving a pooled SD of 3.09 and a mean difference of 0.7 between groups (the latter is used as a proxy of effect size d).

According to these results, we have estimated the following sample size requirements, to achieve 90% power at 0.05% significance level, for each outcome:

- reduction in frequency of acute attacks in final year a sample size of 90 is required for each arm
  - reduction in SUA below the therapeutic target a sample size of 70 patients is required for each arm
- quality of life a sample size of 233 is required for each arm (80% power at 0.05% significance level

Allowing a 10% drop-out rate over the 2 years, this requires a total of **512 patients** (233 plus 23 dropouts in each arm) to provide adequate power for the primary outcome and for 2 of the key secondary outcomes. There are no data on changes in GAQ in response to treatment, but being a disease-specific instrument, we assume that the GAQ will be more sensitive to change than the SF36 and that a total size of 796 will be adequately powered for this outcome.

The total number of GP practices in Nottinghamshire is 170 and the estimated number of registered patients with gout is 10,720 (i.e. an average of 65 patients per GP). A questionnaire will be sent to all patients (unless they have an exclusion criterion) to detect eligible patents. A random sample of those eligible will be selected using the simple random selection after the consent to the trial.

Page **20** of **29** Final version 8 –18 May 2015

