# 2. Secondary outcomes

- Number of acute attacks in preceding year, year 1 and year 2 within each group and between groups
- Number of patients with tophi at baseline, 12 months and 24 months with each group and between groups
- Mean QoL scores (overall, different domain scores of SF36 and the Gout
   Asssessment Questionnaire (GAQ) including the Gout Impact Scale (GIS) of the GAQ.
   at 0, 12 and 24 months within each group and between groups
- Mean change of QoL scores from baseline to 12 months and 24 months within each group and between groups

**Covariates and baseline predictors:** age, gender, body mass index, disease duration, tophi, associated comorbidity etc.

Task allocation and timetable: The Nottingham CTU will undertake randomisation, development of the database for RCT and the web-based data entry platform. CTU will also conduct data monitoring and quality control for the RCT data. Academic Rheumatology will recruit patients, enter the data through a web-based data entry platform for the RCT data and develop an independent database for the observational group. Both datasets are not open for any interim analysis between baseline and 24 months to keep the randomisation. Analysis will start after 24 months when the data has been fully completed, quality checked over and closed. Analysis for clinical effectiveness (efficacy and side effects) will be completed in 3 months after the closing date of the data. Analysis for cost-effectiveness will be completed in 12 months, as it requires acquisition of additional data for cost. In brief:

- Recruitment 8 months
- RCT and observation 24 months
- Results for clinical effectiveness 3 months
- Results for cost-effectiveness 12 months

Economic Analyses Plan.

Two economic analyses are planned: the first being an economic analysis alongside the RCT and the second modelling the costs and benefits over a longer time horizon. The base case in both models would use an NHS perspective, with a societal perspective (that include indirect costs such as lost productivity) being undertaken in a sensitivity analysis.

Economic analysis alongside the RCT

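### The entry criteria do not enforce the untreated or under-treated population of the objective; about a third of participants may already be at the urate target at randomisation, and the plan does not separate reaching it from staying there

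*Supplement*

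**What the plan says.** **Objective (protocol version 8, Primary objective; similarly the Synopsis).** "To determine in community-based patients with untreated or under treated gout the effectiveness and cost effectiveness of a nurse-led complex intervention".

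**Entry rules (Inclusion criteria, Exclusion criteria).** "All Adults aged 21 and over with a GP given diagnosis of gout, confirmed following telephone interview", to check the ACR criteria, and "Nurse intervention and standard care groups (RCT) at least one acute attack of gout in the previous year". The exclusions are inability to give consent and "GPs will be asked not to contact people with terminal or mental illness". Neither list mentions SUA or ULT.

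**Recruitment.** The GP-route questionnaire asks about current drugs, but no eligibility rule uses the answer. The advertising route checks diagnosis and a recent attack. Allocation follows directly after consent at the first nurse visit (Randomization; Informed consent), and SUA plays no part in selection.

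**Primary endpoint.** "Percentage of patients who hit the therapeutic target at end of year 2", defined as SUA below 360 µmol/L. It is a threshold, not a change from baseline.

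**Analysis plan (17 July 2013).** It tabulates the percentage at target and mean SUA at 0, 12 and 24 months, SUA change, and an NNT (Outcome measures). One multilevel model takes all three time points as responses (Principles of analysis). The named covariates are "age, gender, body mass index, disease duration, tophi, associated comorbidity etc". Baseline SUA and baseline ULT are not among them. The only subgroup analysis mentioned is economic, conditional, and by unspecified patient types.

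**The concern.** A patient on ULT with an SUA of 300 and one attack in the past year is eligible, and so is a patient on no ULT with an SUA of 340. Both meet the primary endpoint on the day they enter and can only keep it or lose it. If such patients are common, each arm's 24-month percentage adds two different things: above-target patients brought to target, and patients who started there and stayed.

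What is at stake is interpretation. The nurse-arm percentage would overstate how often above-target patients reach target. The risk difference and NNT would describe a mixture that the objective does not describe. Leaving baseline SUA out of the named covariates also gives up precision, since it is an obvious predictor of later SUA.

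**Working it through.** **The plan's own figures.** The documents give no share at target at baseline, so there is nothing to reproduce and it must be derived. The plan does state 70 per arm for this outcome. A comparison of 25% with 77% at 90% power and two-sided 5% gives 18 per arm (21 with continuity correction), so 70 does not reproduce. That is a separate matter; 70 serves below only as the plan's stated requirement.

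**Inputs (Power calculations, survey of 250 gout patients).**
- On ULT: 30%.
- Attack in the previous year: "the rate for acute attacks in the previous year was 32% for patients on ULT and 57% for patients on no ULT".
- SUA above 360: 23% on ULT and 75% off ULT, so at or below 360: 77% and 25%.

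The survey cut is above 360 and the endpoint is below 360; the difference is negligible.

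**Step 1. ULT use among those with an attack.**
0.30 × 0.32 / (0.30 × 0.32 + 0.70 × 0.57) = 0.096 / 0.495 = 19.4%.

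**Step 2. Share at target at entry**, assuming SUA is unrelated to recent attacks within each ULT group.
- On ULT and at target: 0.194 × 0.77 = 14.9%.
- Not on ULT and at target: 0.806 × 0.25 = 20.2%.
- Total: 35.1%, or 0.351 × 512 ≈ 180 participants.

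**Step 3. Range.** The low case assumes that patients with a recent attack are less often at target: 50% on ULT and 10% off. These two rates are assumptions, not document figures. The high case uses the survey rates without conditioning on an attack.

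| Case | On ULT | On ULT, at target | Not on ULT, at target | Total at target | Of 512 |
|---|---|---|---|---|---|
| Low (assumed 50%, 10%) | 19.4% | 9.7% | 8.1% | 17.8% | 91 |
| Survey rates, given an attack | 19.4% | 14.9% | 20.2% | 35.1% | 180 |
| Survey rates, no conditioning | 30% | 23.1% | 17.5% | 40.6% | 208 |

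**Step 4. Effect on the contrast.** With b the share at target at entry,

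RD(all) = (1 − b) × RD(attainment) + b × RD(maintenance).

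If the arms did not differ in maintenance, RD(all) would be 0.65 of the attainment difference (0.59 to 0.82 over the range), and the NNT 1/0.65 ≈ 1.5 times as large (1.2 to 1.7). A maintenance benefit in the nurse arm would shrink this gap.

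**Step 5. Power.** At 230 completers per arm (256 × 0.90), power for 35% against 77% exceeds 99%; 28 per arm would do.

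**Step 6. Size of an attainment comparison.** 230 × (1 − b) = 149 per arm at 35.1%, 137 at 40.6% and 189 at 17.8%. All exceed 70.

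**The case against.** **At target is not the same as outside the objective.** The objective covers untreated or under-treated gout. Someone on no ULT with an SUA of 340 is untreated on an ordinary reading. In the central case that describes 20 of the 35 points, leaving about 85% of participants untreated or above target. This stands. A reader might infer that the trial answers a different question from the one stated; the documents do not support that. They define neither term, so the boundary cannot be fixed exactly.

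**35% is probably high.** The protocol's own account of gout has crystals forming above saturation and then provoking attacks, so patients with a recent attack should be at target less often than the survey average. This also stands, and is why the range reaches down to 18%.

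**The plan already shows baseline status.** The percentage at target at baseline will be tabulated with the 24-month figure, and mean SUA change is compared between arms. The covariate list is open-ended, and the protocol allows baseline adjustment as appropriate. This is partly right: a careful reader will see the baseline share. But two marginal percentages do not show who was converted and who was maintained, and an open-ended list does not pre-specify the main predictor.

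**It may be a pragmatic choice.** The recruitment section restates the aim for community-based patients with gout, with no treatment qualifier, which matches the criteria. That supports rewording the objective rather than changing enrolment.

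**Dilution in points.** A reader might want a specific pair of risk differences for above-target and all participants. That needs a control-arm rate and a maintenance effect, neither of which the documents give, so only the ratio in Step 4, under its stated assumption, can be shown.

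**Conclusion.** The point holds as a mismatch of wording and a gap in the analysis. The criteria do not enforce the objective's population, and by the protocol's own survey about 35% of participants (18% to 41%) may be at target when randomised. About 15% of participants would be on ULT and at target, and so outside the objective (10% to 23% across the same cases).

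The central figure rests on the survey resembling the enrolled population and on SUA being unrelated to recent attacks within ULT groups. The 15% rests on reading treated and at target as neither untreated nor under-treated.

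There is no bias: the comparison is randomised, and the all-randomised contrast is valid for the patients enrolled. Power is not threatened. What suffers is the meaning of the 24-month percentages and the NNT, and some precision. The change is worth making because it is cheap.

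**What to change.** Leave enrolment as it is.

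1. **Adjust the primary comparison.** In the analysis plan, name baseline SUA (or at-target status) and baseline ULT use as covariates for the 24-month primary comparison. The current model has baseline SUA or target status as a response row, so take that row out when it becomes a covariate; otherwise one measurement serves as both outcome and predictor. Baseline ULT raises no such problem.

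2. **Separate attainment from maintenance.** Keep the all-randomised intention-to-treat result as primary. Beside it, pre-specify the primary endpoint and NNT by baseline target status: attainment for participants not at target at entry, maintenance for those at target. Use the same threshold definition as the primary endpoint. Do not present the attainment subset as the objective's population, because it leaves out untreated patients who start below 360.

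3. **Reconcile the wording.** Bring the Synopsis and Primary objective into line with the Inclusion criteria. The recruitment section already describes the population without the treatment qualifier.

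**Cost.** Analysis-plan text, one restructured model and one extra table. Baseline SUA and drug history are already recorded in both arms. The attainment comparison uses roughly 60% to 80% of the sample, still above the 70 per arm the protocol states for this outcome. The maintenance group will be smaller and its estimates less precise.

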### **Exclusion criteria**

- Inability to give informed consent
- GPs will be asked not to contact people with terminal or mental illness

### **Expected duration of participant participation**

Study participants will be participating in the trial for 2 years.

### Removal of participants from therapy or assessments

This study involves comparison between a nurse-led "best practice" care and ongoing standard care. Participants will be withdrawn from the study if they lose the capacity to consent. Participants may also leave the study in the following circumstances:

- 1] if they move from the area during the 2 year period or wish to change their GP practice
- 2] if they withdraw their consent to remain under observation within the study

The participants will be made aware that this will not affect their future care. Participants will be made aware (via the information sheet and consent form) that should they withdraw the data collected to date cannot be erased and may still be used in the final analysis.

### Informed consent

All participants in the RCT will provide written informed consent. Participants invited into the RCT will receive a letter of invitation together with an information sheet explaining that the trial will compare two methods of delivering gout care - one primarily led by a nurse and one primarily led by their GP (i.e. ongoing standard care). The research nurse will be able to answer any immediate questions they may have prior to booking an appointment to see the patient at their GP surgery or in their home. At the nurse visit participants will have the opportunity to ask any further questions prior to giving their full informed signed consent. Randomisation will occur at this stage.

Informed consent will be collected from each participant before they undergo any interventions (including physical examination and history taking) related to the study. One copy of this will be kept by the participant and one will be kept by the Investigator.

Page **14** of **29** Final version 8 –18 May 2015

Should there be any subsequent amendment to the final protocol, which might affect a participant's participation in the trial, continuing consent will be obtained using an amended Consent form which will be signed by the participant.

### **Future contact**

Participants will be asked if they are willing for their contact details to be stored on a secure database in Academic Rheumatology, to enable them to be informed of future studies undertaken by the department for which they might be suitable. Participant data will be kept up-to-date in accordance with Data Protection Act, 1998. The consent form includes an optional clause asking participants to confirm whether they are happy for their personal details to be retained for this purpose - if not their contact details will be destroyed at the end of this study after it is no longer necessary to contact them.

